6. TRIAL PROCEDURES

6.1 Pre-intervention assessments

We will keep careful records about eligible referrals and consent to participate, these will inform intervention adherence and acceptability measures. We will document these in a CONSORT flow diagram. We will collect most interview data from hostel staff, to reduce resident burden and ensure that data is comparable if the degree of impairment of the resident prevents them completing questionnaires. Baseline appointments will take place at the hostel in person. At the baseline appointment, researchers will obtain written or audio-recorded verbal informed consent to take part in the study from staff (Phase one and two) and older residents with memory problems (phase two) who have capacity (or a personal/nominated consultee will sign for older people who lack capacity to consent). Recruitment, approach and consenting procedures are detailed above in sections 5.3, 5.4 and 5.5). Hostel staff will complete outcome assessments and senior staff familiar with participating older residents will complete the proxy measures.

All pre-treatment procedures will be carried out as specified in the schedule of assessments (appendix 1).

6.2 Registration Procedures

Participant registration will be undertaken centrally by the coordinating trial team.

Following participant consent, and confirmation of eligibility (see section 7.1 for pre-treatment assessments) a participation trial identification number will be generated centrally by the coordinating trial team. The hostel will be informed that a resident is enrolled in the study (phase two).

6.3Baseline and Intervention Procedures

6.3.1 Baseline data

Sociodemographic and background data

The following data will be collected from all participants recruited into phases one and two at the baseline assessment:

Information about the hostel

Provider, resident and staff numbers, support level, accessibility, admission criteria, funding arrangements, alcohol permitted, permanent and temporary staffing numbers, key working, available and mandatory training and in reach health and social care services available. Although not randomising hostels, PR will survey consenting managers regarding hypothetical willingness to be randomised in a future study.

Information about hostel staff

- 1. Age, sex, ethnicity, first language.
- 2. Role, time in current role, years of experience, work pattern, employment history in homelessness and dementia, qualifications and last six months training.

At phase 2 the following information will also be collected:

Information about the person living with memory problems

- 1. Age, sex, ethnicity, first language.
- 2. Education, last occupation, contact with friends/family.
- 3. Physical and mental health history, alcohol and substance use.
- 4. If diagnosed, type of dementia, time since diagnosis.
- 5. Accommodation history, time in hostel.

Quantitative outcomes (phase two only)

In phase two, all outcomes intended for the full RCT will be collected at baseline (pre) and six months (post) intervention delivery. The primary outcomes for this feasibility trial will be:

- The proportion of hostel staff participants adhering to intervention (attending at least 4/6 sessions)
- The proportion of participating staff completing candidate primary outcome for a full trial at follow up (Sense of Competence in Dementia Care Staff (SCIDS) or Maslach Burnout Inventory (MBI)).

Hostel staff will be asked to complete at baseline and six months after baseline:

Sense of Competence in Dementia Care Scale (35): This asks staff 17 questions to find out about how able they feel to deliver person-centred care. Adequate psychometric properties are reported.

Maslach Burnout Inventory (36). This questionnaire measures burnout and is widely validated and used in staff working with residents with dementia(37) and in homelessness(38). It comprises 22 items scored on a 0 - 6 Likert Scale.

The staff member working most closely with each participating resident will be asked to complete the following measures:

Disability Assessment for Dementia scale (DADS), a standard measure of functional independence (basic and instrumental activities of daily living) (39).

Brief Neuropsychiatric Inventory Scale (NPI-Q)(40): A 12 domain survey assessing neuropsychiatric symptomatology. The NPI-Q provides symptom Severity and Distress ratings for each symptom reported, and total Severity and Distress scores reflecting the sum of individual domain scores.

Modified Client Service Receipt Inventory (CSRI)(41): A proxy questionnaire asking about health and social care service use information in the past 4 months for the participant. This will enable us to calculate intervention and other costs.

EQ-5D 5 level (EQ-5D-5L)(42) proxy: A generic measure of health related quality of life.

People living with memory problems will be asked to complete at baseline and six months after baseline:

EQ-5D 5 level (EQ-5D-5L)(42): A generic measure of health related quality of life.

6.3.2 Intervention Procedures

Details of the HOME intervention are in section 6.1 above. Researchers and nominated hostel staff will be trained and supervised to deliver the HOME intervention to groups of hostel staff. Researchers will consult with hostel managers to arrange one series (for phase one) and 2-4 series (for phase two) of six intervention sessions (every 1-2 weeks) for groups of 6-8 hostel workers. Attendance at training sessions will be monitored and if a hostel worker is unable to attend a session, they will be offered an alternative session with a different group.

Intervention measures: We will keep records of staff attendance at intervention sessions, reasons for non-attendance or cancellation, time taken delivering intervention, hostel-based action plans, attendance at implementation visits, supervision and training and facilitators. We will audio record a randomly selected intervention sessions for each group in each hostel to assess facilitator fidelity to the intervention.

6.4 Subsequent assessments and procedures

Phase one: The focus group will take place at three months, within one month of completion of the final session. We will also invite researchers who have delivered the HOME intervention to take part in a structured qualitative interview to understand their experiences. At six months, following the completion of the implementation visits we will conduct a structured qualitative interview with the staff who received the intervention.

Phase two: The follow up assessments will take place at six months, by which time all intervention sessions and implementation visits will have been completed. Please see section 7.3.1 for a list of follow-up measures. We will also conduct qualitative interviews with 8-10 staff participants (including managers) to evaluate their experiences of receiving the interventions. We will invite researchers who have delivered the intervention to take part in a structured qualitative interview to understand their experiences.

At six month follow up we will collect information on staff turnover in each hostel and if at follow-up participants are no longer resident, we will collect information about where they are (e.g., settled community placement, residential care, hospital, deceased, missing).

A schedule of all trial assessments and procedures is set out in Appendix 1.

6.5 Discontinuation/withdrawal of participants

Researchers will explain to the participant at the point of consent and at the baseline assessment (if at separate times) that they are free to withdraw from the study at any time without this having any effect on their care or employment and without having to give a reason. Any data that has been collected up to the point of withdrawal will be retained and used in the study unless the participant asks for it to be withdrawn. After analysis withdrawal of data will not be possible. No further information will be collected from the participant after withdrawal. Participant withdrawal will be documented in the Case Report Forms (CRFs) and the hostel staff informed. Participants who withdraw from the study will not be replaced. Participants would be withdrawn from the study if:

- They actively stated that they no longer want to take part
- If the staff member loses capacity
- If a participant with memory problems who had capacity at the start of the study loses capacity and a personal/nominated consultee cannot be identified.

6.6 Definition of End of Trial

The expected duration of the trial is 25 months from recruitment of the first participant.

Phase one: The end of the study period will be when the final participant has completed the qualitative focus group/interview. Data will then be analysed and used to modify the final intervention manual and training programme ready for testing in the feasibility RCT.

Phase two: The end of the study period will be when the final participant has completed the followup outcome measures. Data will then be analysed and used to modify the final intervention manual and training programme ready for testing in a full RCT.

7. FINANCE AND SUPPLY OF EQUIPMENT

The research costs for the study have been supported by a National Institute for Health and Care Research (NIHR) Advanced Fellowship (NIHR300844) - £854,616.00 Date of award 01.03.21. The study funding has been reviewed by the UCL Research Office and deemed sufficient to cover the requirements of the study. There are no NHS costs associated with this study.

8. DATA MANAGEMENT

8.1 Confidentiality

The study is compliant with the requirements of General Data Protection Regulation (2016/679) and the Data Protection Act (2018). All investigators and study site staff will comply with the requirements of the General Data Protection Regulation (2016/679) with regards to the collection, storage, processing and disclosure of personal information, and will uphold the Act's core principles. UCL is the data controller; the UCL Data Protection Officer is [[contact]]. The data processors are [name] and those detailed in delegation log. The study will be collecting the following personal data: names, addresses, email addresses, telephone numbers, dates of birth, professional statuses, ethnicity, diagnosis.

Where data is coming from?

Participant names and contact details will be obtained from the hostel manager once verbal consent has been given to share this information. The demographic and outcome data will be obtained directly from participants. Some demographic and clinical information will be obtained from hostel records for example to aid completion of the CSRI or demographic data. This is specified in Consent/consultee declaration forms.

What personal data is being collected?

The personal data being collected will include identifiable data (1. name and address to enable recontact; 2. Demographic details including age, gender, ethnicity, employment, education, first language, housing history, physical and mental health status and substance use; 3. Audio recordings which will likely contain participant's first name and possible other identifiers until they are transcribed and cleaned). Each participant will be assigned a participant ID number and demographic and outcome data will be pseudo-anonymised and stored separately from the subject name or address.

Where will the data be recorded or stored?

Personal data needed to re-contact participants for follow up assessments and intervention sessions will be held securely on password protected excel spreadsheets on password-protected computers at UCL and accessed only by the UCL research team.

Consent forms will be held manually at UCL Maple House under the supervision of CI [name]. The data will be held in a locked filing cabinet in UCL Maple House, only [name] and named members of the research team will have access, we will abide by UCL data protection policies.

The CRFs will not bear the participant's name or other personal identifiable data and will be stored in a separate locked filing cabinet to the consent forms. The participant's initials, date of birth and trial identification number, will be used for identification and this will be clearly explained to the participant in the participant information sheet. Participant consent for this will be sought. Data from the paper CRFs will be entered by the study team into the password protected study database and stored on password protected computers on UCL servers.

Researchers will have their own GDPR compliant audio recording devices. The recordings of qualitative interviews and focus groups will be uploaded through a secure server to a UCL approved provider for interview transcription. They will be transferred back through the same server when transcribed. Researchers who conducted the interviews will read them through and remove all identifiable data. Once they have done this, they will destroy the non-anonymised transcript and recording. Audio recorded intervention sessions will be stored password protected on password protected computers on UCL servers. Once the recordings of sessions have been listened to and fidelity to the intervention rated, these recordings will be deleted.

Who will have access to the data?

Only [name], CI, and research assistants and other members of the research team (including associated PhD and MSc students) will have access to electronically and manually stored data. Only UCL substantive employees and students working under their supervision will have access. It will be the responsibility of the investigator and delegated members of the research team to ensure the accuracy of all data entered in the CRFs.

Data will not be transferred outside UCL computer systems unless in aggregated, anonymised form. It will be disseminated in aggregated, anonymised form in research publications and conference presentations.

How long with the data be stored for?

We will store personal data for up to three years to enable us to send participants a summary of the results and contact them about future research studies. Electronic data will be deleted after this time and paper copies will be destroyed via confidential waste.

Audio-recordings will be stored as stated above, only until transcriptions have been checked. Other data will be saved for 20 years in line with UCL policies for archiving.

The research data will be well-managed and submitted for archiving as per NIHR requirements, maximising potential for further research. All data will be managed within UCL information security policies https://www.ucl.ac.uk/informationsecurity/policy.

8.2 Data collection tools and source document identification

A data management plan will be created which will include details of the data collection tools, methods of completing case report forms, sign off completed CRFs, source document identification and methods to maximise completeness of data collection.

It will be the responsibility of the investigator, PR, to ensure the accuracy of all data entered in the CRFs. The delegation log will identify all those personnel with responsibilities for data collection and handling, including those who have access to the trial database.

Data will be collected from sites on trial specific CRFs. Data collected for the study will be entered into the paper CRFs by the central team researchers and brought back to UCL within 5 days of a participant visit and then entered into the online database.

8.3 Completing Case Report Forms

All CRFs will be completed and signed by staff that are listed on the site staff delegation log and authorised by the CI to perform this duty. The CI is responsible for the accuracy of all data reported in the CRF.

Once completed the original CRFs must be brought to UCL Maple House. The CRFs must be returned within five days of the participant visit.

8.4 Data Handling

In the study, all will be collected from participants in accordance with the consent form, information sheet and sections 7 of this protocol. All data will be collected and handled in accordance with GDPR & UK Data Protection Act (2018)

The data collected in the CRFs and qualitative data will be appropriately stored at UCL Maple House for data analysis and UCL will act as the data controller of such data for the study.

[name] and those detailed in the delegation log will process, store and dispose of data in accordance with all applicable legal and regulatory requirements, including the Data Protection Act 2018 and any amendments thereto.

No data will be transferred to any party not identified in this protocol and are not to be processed and/or transferred other than in accordance with the participant's consent.

Direct access to the data will be granted to authorised representatives from the Sponsor, host institution and the regulatory authorities to permit study-related monitoring, audits and inspections, in line with participant consent.

8.5 Personal Data breaches

Personal data breaches will be immediately reported to the UCL Information Security Group (ISG) and the UCL Data Protection Officer [[contact]], and to the Sponsor via the UCL JRO research incident reporting form (as per form and guidance: https://www.ucl.ac.uk/legal-services/guidance/reporting-loss-personal-data). The following information will be provided: full details as to the nature of the breach, an indication as to the volume of material involved, and the sensitivity of the breach (and any timeframes that apply). Sites will additionally follow their Trust incident reporting mechanisms and will document this within their TMF/ISFs.

9. STATISTICAL CONSIDERATIONS

9.1Primary outcome

Phase one:

- The proportion of participating staff adhering to the intervention (attending at least 4/6 sessions).
- The acceptability and perceived usefulness of the intervention established through focus group and qualitative interviews to inform revision of the intervention for the feasibility trial.

Phase two: The primary outcomes for the feasibility trial will be:

- The proportion of hostel staff participants adhering to intervention (attending at least 4/6 sessions)
- The proportion of participating staff completing candidate primary outcome for a full trial at follow up (SCIDS or MBI).

9.2Secondary outcome(s)

- The proportion of participating older people for whom primary outcome for the main trial is completed at follow up (EQ5D-5L / DADS).
- The estimated cost of delivering the intervention to inform their feasibility in a future full trial.
- The acceptability of and fidelity to the intervention established through a mixed methods process evaluation to assess intervention acceptability and required refinements.

9.3Sample size calculation

Phase two only: With 40 staff participants we will achieve the following 95% confidence interval for expected adherence and participation estimates:

1. Proportion of participants adhering to intervention (attending at least 4/6 group or individual sessions) (expected value 75%, 95% confidence interval: 59-87%).

2. Proportion of staff for whom potential staff outcomes (SCIDS or MBI) completed at 6-month followup (75%, 95% confidence interval = 59-87%).

With these numbers we will be able to estimate parameters with sufficient precision to inform continuation to an RCT. "Stop go" criteria will be related to intervention adherence:

- >=70%: go to main trial
- 60-69: modified trial to increase adherence
- <60: do not progress to main trial using this model.

This sample size will also be sufficient to estimate the standard deviation required for the sample size calculation in the main trial (43, 44).

9.4Planned recruitment rate

We estimate that recruitment referral rate will be approximately 10 potential staff participants month; 5 participants will be suitable and 4 will agree to participate and follow-up will be approximately 70%.

9.5Statistical analysis

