5.3 Recruitment

Recruitment will be in London and Southern England across culturally and socioeconomically diverse semi-rural and urban sites. Participants with memory problems and hostel staff and managers will be recruited from third sector homelessness service providers by UCL staff. In addition to our agreed collaborations with third sector Homelessness organisations, we will liaise with the Homelessness Research Programme in the NIHR Policy Research Unit in Health and Social Care Workforce at King's College London and the Faculty for Homeless and Inclusion Health to assist us in identifying homelessness hostels. Consent logs will be completed by UCL researchers to record eligibility / ineligibility and participation/non-participation.

Phase one: The research team will recruit one hostel (through contacting the hostel manager) and will seek to recruit around 8 eligible staff over a four-week recruitment period. Hostel managers will approach 8 hostel staff to invite them to take part. We will not recruit a hostel where the manager cannot identify at least 8 staff who would be asked to take part in the study, and where there are less than 5 residents aged fifty and over who the managers and staff feel have memory impairment (there will be no formal screening of residents for phase one as we are not recruiting residents for this phase).

Phase two: We will recruit up to five hostels (not including the hostel recruited in phase one), from which we plan to recruit all (estimated total across all agencies: 40) hostel staff, and all (estimated total: 40) hostel residents aged fifty years and over living with a dementia diagnosis or screening positive for significant memory disorder on the NPC (32).

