The initial approach in phase one and phase two will be by the CI (PR) to hostel managers. We are in contact with several organisations through the wider project and specifically with a wide range of hostels that have participated in stream 1 of the HOME study. The CI or HOME researcher will meet with interested hostel managers to explain the study. Managers who are interested in taking part will be asked to approach staff and residents to ascertain whether they are interested in taking part in the study. If they are, we will carry out the processes below. For consent and assessment of capacity please refer to section 5.5. All potential participants will be given or sent a study leaflet and the Participant Information Sheet (PIS) and asked for their permission for a researcher to contact them. Recruitment will take place over one year. We will not recruit a hostel where the manager cannot identify at least 15 staff (this is more than in phase one as we want to recruit a larger sample overall) who would be asked to attend the training (whether or not they agree to take part in the study), and the hostel manager agrees to delivery of the HOME training as part of their core training, or where there are not at least 8 residents who have a dementia diagnosis or significant memory disorder (NPC Score $2\ge$).

1. Hostel managers: We will initially approach hostel managers to invite them to participate. We will aim to recruit hostels via organisations that have already participated in our earlier qualitative study as well as through existing relationships with homelessness service providers. We will obtain consent from the hostel managers for the hostel participation in the observations (see Section 5.5). If they agree to hostel participation, we will elicit their written, informed consent or (audio-recorded) verbal consent for hostel.

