HOME Intervention facilitated group sessions: The HOME intervention will be delivered to all hostel staff who work weekday, daytime shifts and provide direct support to some residents with memory problems within participating hostels. It will be delivered to small groups of around 6-8 staff by pairs comprising one trained researcher and one trained senior hostel worker. Each of these groups will receive six training sessions, which will each last 2 hours, with a break when drinks and snacks will be provided. Groups will be 1-2 weeks apart over a three-month period. Hostel staff will be asked to try and attend the same group for all six of the sessions, but they can attend a different group if needed. The manager may attend different groups for each session, so that hostel workers have sessions with and without the manager present. The session content will be written in a manual so that it is delivered the same way each time and so that hostel workers have their own copy to keep and make personalised notes in. Those who attend all sessions will receive a certificate. The six sessions will be:

- 1. Introduction to understanding memory problems
- 2. Communicating with people with memory problems
- 3. Trauma informed understanding and managing distress behaviours and unmet needs.

- 4. Strategies to support functioning, meaningful interaction & harm minimisation
- 5. Understanding and assessing capacity and safeguarding
- 6. Keeping it going and developing individual and hostel wide plans

Sessions will be informed by a collaborative and reflective practice-based approach, valuing the expertise of participating staff and the lived experiences of the older people in their care, drawing on individual case discussions. The groups will be interactive and include between session tasks for staff.

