9.5.2 Phase two

Assessment of outcomes

The statistical analyses will be described in a predefined analysis plan. The main analyses are: Baseline data will be summarised using means (with SD), medians (with interquartile ranges), counts and proportions, as appropriate, to describe characteristics. We will produce a consort diagram to describe the flow of participants through the trial and consider potential bias arising from dropouts and losses to follow-up.

1. We will calculate the proportion of staff adhering to the intervention (attending a predetermined number of sessions) with 95% confidence intervals.

2. The EQ-5D-5L, SCIDS and MBI scores will be summarised to provide distributional information and obtain estimates of SDs, and correlation needed for main trial's sample size calculation.

3. Referral rates, drop-out and loss to follow-up rates will be calculated with 95% confidence intervals.

4. Other staff and resident outcome data will be summarised using appropriate estimates with 95% confidence intervals.

Intervention costs

To calculate the unit costs of intervention delivery we will include: the hourly cost of training and supervising facilitators; hours spent by facilitators delivering training and supervision in hostels; hours spent by staff engaging in the intervention; capital travel and materials costs; and numbers of residents supported. We will obtain staff costs from published sources (47).

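### The 59–87% precision stated in Protocol section 9.3 treats 40 staff from at most five hostels as independent, so it is optimistic for any positive within-hostel correlation

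*Protocol*

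**What the plan says.** Section 9.3 introduces its figures with "With 40 staff participants we will achieve the following 95% confidence interval for expected adherence and participation estimates". For adherence the entry is "Proportion of participants adhering to intervention (attending at least 4/6 group or individual sessions) (expected value 75%, 95% confidence interval: 59-87" (per cent). The second phase-two primary outcome, completion of a candidate staff measure at six months, has the same expected value and the same interval. The section then concludes that these numbers give enough precision to inform the decision on a later RCT. It states no ICC, design effect or other allowance for clustering.

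Other sections describe where the 40 staff come from:

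- Section 5.3: "We will recruit up to five hostels (not including the hostel recruited in phase one").
- Section 5.3 also sets a minimum hostel size: "We will not recruit a hostel where the manager cannot identify at least 15 staff".
- Section 5.6, on delivery: "It will be delivered to small groups of around 6-8 staff by pairs comprising one trained researcher and one trained senior hostel worker".
- Section 5.6 also has the team agree with each hostel manager how to maximise attendance, including suitable days and times. Section 5.4 places attendance within paid working hours.
- Section 3.1 names a cluster RCT as the trial that this study prepares.

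For the analysis, section 9.5.2 says "We will calculate the proportion of staff adhering to the intervention (attending a predetermined number of sessions) with 95% confidence intervals". It names no interval method and refers the detail to a separate analysis plan.

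**The concern.** Staff in one hostel share a manager, a rota, a hostel champion who co-leads the sessions, and an agreed attendance plan. If these affect who reaches four sessions, or who is still in post at six months, two colleagues from one hostel carry less information than two staff from different hostels. The effective sample size is then below 40, and an interval computed as if all 40 were independent is too narrow.

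What is at stake is a property that the protocol tells its readers the design will deliver. Section 9.3 presents the interval as achieved with 40 staff and rests its statement of sufficient precision on it. Both phase-two primary outcomes are affected.

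**Working it through.** **Inputs from the Protocol.** n = 40 staff; expected proportion 75% (30/40) for both outcomes; stated 95% interval 59–87% (section 9.3). At most five hostels, so on average at least 40/5 = 8 staff per hostel (section 5.3). At least 15 staff identified per hostel (section 5.3).

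**Could it be three hostels?** Three hostels at the minimum give 3 × 15 = 45 staff. At the agreement rate implied by section 9.4 (4 of every 5 suitable staff), that yields 45 × 0.8 = 36. Three hostels a little above the minimum would therefore supply 40. Three is possible under the recruitment rule, not certain.

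**Input that must be assumed.** The Protocol gives no ICC. A range of 0.01 to 0.20 is used here. Hostels are taken as equal in size.

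**Step 1: reproduce the stated figure.** For 30/40 as independent observations:

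| Method | 95% interval |
|---|---|
| Exact (Clopper–Pearson) | 58.8–87.3% |
| Wilson | 59.8–85.8% |
| Wald | 61.6–88.4% |

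Only the exact interval rounds to 59–87%. The printed arithmetic is right for independent data, and the independence assumption can be read off the figure.

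**Step 2: allow for hostel.** With m staff per hostel:

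- design effect = 1 + (m − 1) × ICC
- effective n = 40 / design effect
- interval = exact interval for 75% at the effective n

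Worked example, five hostels, ICC 0.10: design effect = 1 + 7 × 0.10 = 1.70; effective n = 40/1.70 = 23.5; interval 53–90%.

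| Hostels (m) | ICC | Design effect | Effective n | 95% interval |
|---|---|---|---|---|
| 5 (8) | 0.01 | 1.07 | 37.4 | 58–88% |
| 5 (8) | 0.05 | 1.35 | 29.6 | 56–89% |
| 5 (8) | 0.10 | 1.70 | 23.5 | 53–90% |
| 5 (8) | 0.20 | 2.40 | 16.7 | 48–92% |
| 3 (13.3) | 0.05 | 1.62 | 24.7 | 54–90% |
| 3 (13.3) | 0.10 | 2.23 | 17.9 | 49–92% |

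With five hostels the full width grows from 28.5 percentage points at ICC 0 to about 33 at ICC 0.05, 37 at 0.10 and 44 at 0.20.

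**Step 3: the choice of method also matters.** A t interval on hostel proportions with five hostels (4 degrees of freedom) is 0.75 ± 2.776 × √(0.1875/40 × design effect). That gives 56–94% at ICC 0, 53–97% at 0.05 and 50–100% at 0.10. Part of that widening comes from having only five clusters and would be present at ICC 0. Precision stated by one method would therefore not describe an analysis done by the other.

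**The case against.** The strongest reply is that the size is unknown and may be small. At ICC 0.01 with five hostels the interval is 58–88%, hardly different from the printed one. The exact interval is also conservative. In simulation (true proportion 75%, five hostels of eight), an unadjusted exact interval covers the truth 97% of the time at ICC 0.01 and 94% at 0.05; it falls clearly short only at about 0.10 (91%) and 0.20 (84%). This stands, and it limits the severity. It does not rescue the claim, because section 9.3 states the precision without condition and the design gives reasons to expect some correlation. With three hostels, coverage is already 92% at ICC 0.05 and 85% at 0.10.

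A reader might go further and infer that the intervals planned in section 9.5.2 are themselves too narrow. The Protocol does not show this. That section fixes no method and defers to an analysis plan that is not at hand, which may well allow for hostel. Its second item even plans to estimate a correlation for the main trial's sample size, although that concerns scores rather than adherence and its type is not stated.

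A reader might also infer that the stop/go decision is compromised by the narrow interval. The bands in section 9.3 (70% or more, 60–69%, below 60%) are set on the adherence percentage and refer to no confidence limit, so a wider interval changes no decision as written. The printed 59–87% already reaches into all three bands.

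**Conclusion.** The concern holds for section 9.3 and should be fixed. The interval of 59–87%, stated for both phase-two primary outcomes, is correct only if 40 staff nested in at most five hostels respond independently. For any positive ICC the precision is worse than stated. The difference is negligible near ICC 0.01 and becomes material from about 0.05, or with fewer than five hostels: 56–89% (five hostels) or 54–90% (three) at ICC 0.05, and 53–90% or 49–92% at ICC 0.10. These figures rest on an assumed ICC range, equal hostel sizes and the exact interval at the effective n. The fault is an unstated assumption, not an arithmetical slip. It bears on the stated precision, not on the progression rule or on an analysis method that the Protocol leaves open.

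**What to change.** In section 9.3, restate both intervals over an assumed ICC range and a stated number of hostels, giving the effective n for each. The table above can serve if the exact interval at the effective n is the chosen method. Say that the ICC is assumed, and qualify the sentence on sufficient precision accordingly.

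State that the reported intervals for adherence and completion will allow for hostel by the same method as the stated precision. If a hostel-level t interval is preferred for the analysis, section 9.3 should quote the wider figures that it gives. Report each hostel's own proportion beside the overall one.

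The cost is wording and a little analysis time, with no extra participants or data. The price is a less favourable precision statement.
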